### 9.1.3 Formulation and Stability

Erdafitinib is a yellow powder. Tablet excipients include mannitol, microcrystalline cellulose, meglumine, croscarmellose sodium and magnesium stearate. Tablets are coated with Opadry AMB II. The agent is available as 3 mg (yellow), 4 mg (orange), and 5 mg (brown) film coated tablets.

The approximate dimensions of the round tablets are in the table below:

Strength	Diameter (mm)	Thickness (width) (mm)
3 mg	7.7 ± 0.2	3.7 ± 0.4
4 mg	8.2 ± 0.2	4.2 ± 0.4
5 mg	8.7 ± 0.2	4.6 ± 0.4

Erdafitinib tablets are provided in 30 count bottles made of high density polyethylene (HDPE), with an induction seal and child resistant cap. Tablets must be dispensed in the original container.

#### Storage

Store intact bottles at controlled room temperature 15°C to 30°C (59°F to 86°F). Tablets must be dispensed in the original container.

If a storage temperature excursion is identified, promptly return erdafitinib to 15°C to 30°C and quarantine the supplies. Provide a detailed report of the excursion (including documentation of temperature monitoring and duration of the excursion) to [[contact]](mailto:[contact]) for determination of suitability.

### **Stability**

Shelf-life dating is printed on the bottle label.

#### **9.1.4 Guidelines for Administration**

See Treatment ([Section 5.0](#)) and Dose Modification ([Section 6.0](#)) sections of the protocol. Administer erdafitinib orally once a day with or without food, at approximately the same time each day. Tablets must be swallowed whole, with approximate 8 ounces of water. Do not crush or chew. If vomiting occurs within 30 minutes of erdafitinib administration, then the dose can be repeated once. If a dose is missed, it can be taken up to 6 hours after the scheduled time. If it has been more than 6 hours since the missed dose, then that dose should be skipped. The next dose should be taken at the usual time.

#### **9.1.5 Supplier**

Erdafitinib is supplied by Johnson & Johnson and distributed by the Division of Cancer Treatment and Diagnosis (DCTD), NCI. **Do not use commercial supply.**

#### **9.1.6 Obtaining the Agent**

NCI supplied agent may be requested by the eligible participating investigator (or their authorized designee) at each participating institution. The CTEP assigned protocol number must be used for ordering all CTEP supplied investigational agents. The responsible investigator at each participating institution must be registered with CTEP, DCTD through an annual submission of FDA form 1572 (Statement of Investigator), NIH Biosketch, Agent Shipment Form, and Financial Disclosure Form (FDF). If there are several participating investigators at one institution, CTEP supplied investigational agents for the study should be ordered under the name of one lead participating investigator at that institution.

**Note: No starter supplies will be provided. Drug orders of erdafitinib (JNJ-42756493) should be placed with CTEP after enrollment and treatment assignment to APEC1621B with consideration for timing of processing and shipping to ensure receipt of drug supply prior to start of protocol therapy.**

Submit agent requests through the PMB Online Agent Order Processing (OAOP) application. Access to OAOP requires the establishment of a CTEP Identity and Access Management (IAM) account and the maintenance of an “active” account status, and a “current” password, and active person registration status. For questions about drug orders, transfers, returns, or accountability, call or email PMB any time. Refer to the PMB’s website for specific policies and guidelines related to agent management. If expedited shipment is required, sites should provide an express courier account through the Online Agent Order Processing (OAOP) application. Provide the patient ID number in the comment box when submitting an order request.

### 9.1.7 **Agent Accountability**

#### **Agent Inventory Records:**

The investigator, or a responsible party designated by the investigator, must maintain a careful record of the receipt, dispensing and final disposition of all agents received from the PMB using the appropriate NCI Investigational Agent (Drug) Accountability Record (DARF) available on the CTEP forms page. Store and maintain separate NCI Investigational Agent Accountability Records for each agent, strength, formulation and ordering investigator on this protocol.

### 9.1.8 **Investigator Brochure Availability**

The current version(s) of the IB(s) for the agent will be accessible to site investigators and research staff through the PMB Online Agent Order Processing (OAOP) application. Access to OAOP requires the establishment of a CTEP IAM account and the maintenance of an “active” account status, a “current” password, and active person registration status. Questions about IB access may be directed to the PMB IB coordinator via email.

## 10.0 **CRITERIA FOR REMOVAL FROM PROTOCOL THERAPY AND OFF STUDY CRITERIA**

### 10.1 **Criteria for Removal from Protocol Therapy**

- a) Clinical (including physical examination or serum tumor markers) or radiographic evidence of progressive disease (See [Section 12](#)).
- b) Adverse Events requiring removal from protocol therapy (See [Section 6](#)).
- c) Refusal of protocol therapy by patient/parent/guardian
- d) Non-compliance that in the opinion of the investigator does not allow for ongoing participation.
- e) Completion of 26 cycles of therapy.
- f) Physician determines it is not in the patient’s best interest.

- g) Repeated eligibility laboratory studies (CBC with differential, bilirubin, ALT (SGPT) or serum creatinine) are outside the parameters required for eligibility prior to the start of protocol therapy (See [Section 8.1](#)).
- h) Study is terminated by Sponsor.
- i) Pregnancy
- j) Patient did not receive protocol treatment after study enrollment

**Patients who are removed from protocol therapy during cycle 1 should continue to have the required observations in [Section 8.1](#) until the originally planned end of the cycle or until all adverse events have resolved per [Section 13.4.4](#), whichever happens LATER. The only exception is with documentation of the patient's withdrawal of consent from the APEC1621SC screening protocol. Patients who are removed from protocol therapy in subsequent cycles should have the necessary observations to ensure adequate clinical care.**

#### 10.2 **Follow-Up Data Submission and APEC1621SC Off Study Criteria**

Patients who are off subprotocol therapy will initially be followed on the therapeutic subprotocol for a 30-day period. During follow-up on the therapeutic subprotocol ongoing adverse events, or adverse events that emerge after the patient is removed from protocol therapy, but within 30 days of the last dose of investigational agent, must be followed and reported via RAVE and CTEP-AERS (if applicable). Upon completion of subprotocol follow-up period, the patient will continue to be followed on the APEC1621SC screening protocol. Follow-up data submission will occur until one of the APEC1621SC Off Study Criteria is met (See Section 10 of APEC1621SC for details); consent is withdrawn or the patient dies or is lost to follow-up.

### 11.0 **STATISTICAL AND ETHICAL CONSIDERATIONS**

#### 11.1 **Sample Size and Study Duration**

APEC1621B will require a minimum of 20 evaluable patients and a maximum of 49 patients, allowing for 15% inevaluability. Assuming an enrollment rate of 4-9 biomarker positive patients per year, the primary cohort of this subprotocol is expected to be completed within 2.7-6 years.

#### 11.2 **Dosing Considerations**

##### **Pediatric MATCH Sub-arm Dosing in the Absence of Pediatric Phase 1 Data**

Please see [Section 5.1](#) for a specific discussion of the dosing of erdafitinib to be used in this study. As there is no prior pediatric phase 1 data for erdafitinib, study investigators have reviewed relevant data with the pharmaceutical partner to identify a drug specific dosing plan for testing in children with recurrent/refractory cancer, and trial participants will be closely monitored to ensure tolerability of the selected dose. Limited pharmacokinetic sampling may be done for patients enrolled on this arm. Since the adult RP2D (8 mg PO once daily) is below the MTD (at least 12 mg PO once daily) the starting dose will be the adult RP2D adjusted for BSA, which is 4.7 mg/m^2/day (8 mg/1.7 m^2) up to a maximum daily dose of 8 mg PO once daily. The dosing for erdafitinib will follow the general Pediatric MATCH subprotocol guidelines as below:

- For agents for which the adult RP2D is below the adult MTD, the adult RP2D (normalized to body surface area or body weight) will be used for evaluation in the Pediatric MATCH, understanding that further dose optimization may be required in a future pediatric study.

### 11.3 Study Design

The primary cohort will employ a single stage A'Hern design of N=20. The agent will be deemed worthy of further study in the relevant subset of patients (i.e. biomarker positive in any histology, biomarker positive in a particular histology, etc) if the decision rule is met. Operating characteristics are shown below.

Cohort	N	Decision Rule	Alpha	Power
Primary biomarker positive	20	≥ 3 responses	10%	90%

Histology-specific biomarker positive expansion cohorts will, by definition, be deemed worthy of further study, since they will have at least 3 responses. The table below shows 90% confidence intervals (Wilson method) for a range of observable response rates.

Cohort Size	Observed Response Rate	90% Confidence Interval
10	30%	13% - 56%
10	40%	19% - 65%
10	50%	27% - 73%

#### 11.3.1 **Primary Cohort:**

APEC1621B will evaluate a primary cohort of 20 mutation-matched (“biomarker positive”) evaluable patients of any histology for the primary study aim of determining the objective response rate (CR/PR according to the response criteria in [Section 12.3](#)) to the agent. Using an A'Hern design with alpha=10%, a sample of N=20 will provide 90% power to detect an improvement in response rate from 5%, if the treatment is ineffective, to 25% if the targeted therapy is sufficiently effective to warrant further study. If there are at least 3 responses out of 20 in the primary cohort, the biomarker/therapy match will be deemed a success.

#### 11.3.2 **Histology-Specific Biomarker Positive Expansion Cohorts:**

If ≥ 3 patients in the primary cohort with the same histology show signs of objective response (CR/PR according to the response criteria in [Section 12.3](#)), a histology-specific biomarker positive expansion cohort will open after the primary cohort is completed to up to 7 evaluable patients for a total sample size of 10 evaluable biomarker positive patients with that histology. This will allow us to estimate more precisely the activity in biomarker positive patients of that histology. See [Appendix VII](#) for a list of target tumor histologies.

We will open up to 3 such expansion cohorts for biomarker positive patients (i.e., if 3 histologies have ≥ 3 responses, we will open a total of 3 expansion cohorts as described above). Note that this can only happen if the response rate in the primary cohort is at least 45% (9/20) and there cannot be more than 21 additional evaluable patients in total for these expansion cohorts.

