#### 11.4 **Methods of Analysis**

Response criteria are described in [Section 12](#). A responder is defined as a patient who achieves a best response of PR or CR on the study. Response rates will be calculated as the percent of evaluable patients who are responders, and confidence intervals will be constructed using the Wilson score interval method. Decision making for A'Hern design cohorts will follow rules described above.

Toxicity tables will be constructed to summarize the observed incidence by type of toxicity and grade. A patient will be counted only once for a given toxicity for the worst grade of that toxicity reported for that patient. Toxicity information recorded will include the type, severity, time of onset, time of resolution, and the probable association with the study regimen.

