#### 11.5 **Evaluability for Response**

Any eligible patient who is enrolled and receives at least one dose of protocol therapy will be considered evaluable for response. Any patient who receives non-protocol anti-cancer therapy during the response evaluation period will be considered a non-responder for the purposes of the statistical rule, unless they show an objective response prior to receiving the non-protocol anti-cancer therapy (in which case they will be considered a responder). Patients who demonstrate a complete or partial response confirmed by central review will be considered to have experienced a response. When opening expansion cohorts, the evaluation period for determination of best response will be the first 6 treatment cycles. All other patients will be considered non-responders. Patients who are not evaluable for response evaluation may be replaced for the purposes of the statistical rule. All patients considered to have a response (CR or PR) must have imaging studies reviewed centrally at the COG. Centers will be notified by the COG about requests for scans of patients with stable disease. Preliminary assessment of activity using institutionally provided tumor measurements will be entered into CDUS quarterly. The central review by COG will be provided as the final reviewed assessment of response when such becomes available.

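### Each histology expansion cohort counts the responders that opened it, so its 10-patient response rate is biased upward, and no separate report of the newly enrolled patients is planned

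*Combined protocol and SAP*

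**What the plan says.** The primary cohort consists of 20 "evaluable patients of any histology for the primary study aim of determining the objective response rate" (11.3.1). How many of the 20 will share a histology is therefore not fixed in advance.

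Under 11.3.2 an expansion cohort opens if 3 or more "patients in the primary cohort with the same histology show signs of objective response". It opens "to up to 7 evaluable patients for a total sample size of 10 evaluable biomarker positive patients with that histology", so at least 3 of the 10 come from the primary cohort. The reason given is: "This will allow us to estimate more precisely the activity in biomarker positive patients of that histology".

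Section 11.3 confirms the pooling: "Histology-specific biomarker positive expansion cohorts will, by definition, be deemed worthy of further study, since they will have at least 3 responses". Of its table it says "The table below shows 90% confidence intervals (Wilson method) for a range of observable response rates", and the table starts at 30%, that is, 3 of 10.

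Section 11.4 defines the rate as responders over evaluable patients and says that "confidence intervals will be constructed using the Wilson score interval method", without stating a level. Section 11.5 adds a time window for the trigger: "When opening expansion cohorts, the evaluation period for determination of best response will be the first 6 treatment cycles".

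Sections 11.3 to 11.5 contain no adjustment for selection, no statement that the pooled rate is selected, and no planned rate for patients enrolled after opening. They do not rule out such a report; they are silent on it.

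**The concern.** The rate for a histology is reported on 10 patients only if the first part of those 10 did well enough. A sample selected on its own outcome overstates the underlying rate, and an interval that ignores the selection does not have its nominal coverage. Estimation is the only purpose given for the expansion, which may enrol up to 21 further evaluable patients over three cohorts. Someone reading a later result of 4/10 with an interval of 19% to 65% would take it as an ordinary sample of 10, although a cohort normally could not have been reported with fewer than 3 responders.

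**Working it through.** **The plan's own figures.** The two-sided 90% Wilson interval (z = 1.645) is

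[p̂ + z²/2n ± z·√(p̂(1−p̂)/n + z²/4n²)] / (1 + z²/n).

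With n = 10 it gives 12.7–55.8% for 3/10, 19.4–64.8% for 4/10 and 26.9–73.1% for 5/10. All three match the table in 11.3. The printed intervals are correct for an unselected sample of 10.

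**Inputs.** From 11.3.2: a trigger of at least 3 responders and a pooled size of 10. From 11.3 and 11.4: the Wilson interval, at 90%. Assumed, because the documents do not give them: n1, and the histology's true rate p. The 25% in 11.3.1 is the target for the any-histology cohort, not for a single histology.

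**Model.** X1 ~ Bin(n1, p) is the number of responders among primary-cohort patients of the histology, conditional on X1 ≥ 3. X2 ~ Bin(10 − n1, p) is the number among the new patients. The reported rate is T/10 with T = X1 + X2. Then

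E[T/10 | opened] = (E[X1 | X1 ≥ 3] + (10 − n1)·p) / 10.

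**By hand, p = 25% and n1 = 3.** X1 must be 3, so the mean is (3 + 7 × 0.25)/10 = 47.5%. The interval covers 25% only when T is 3 or 4, because the lower limit for 5/10 is already 26.9%. Coverage is therefore P(X2 ≤ 1) = 0.1335 + 0.3115 = 0.445.

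**Full enumeration:**

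| True rate | n1 | P(opens) | Mean reported rate | Coverage of 90% interval | Coverage, unselected 10 |
|---|---|---|---|---|---|
| 25% | 3 | 1.6% | 47.5% | 44% | 86.6% |
| 25% | 5 | 10% | 44.1% | 57% | 86.6% |
| 25% | 8 | 32% | 39.5% | 76% | 86.6% |
| 25% | 10 | 47% | 36.9% | 84% | 86.6% |
| 30% | 5 | 16% | 47.0% | 77% | 92.4% |
| 30% | 8 | 45% | 41.9% | 89% | 92.4% |
| 40% | 3 | 6.4% | 58.0% | 71% | 89.9% |
| 40% | 5 | 32% | 53.1% | 84% | 89.9% |
| 40% | 8 | 68% | 47.3% | 92% | 89.9% |

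If n1 = 3 to 10 are taken as equally likely beforehand and weighted by the chance of opening, a true 25% gives a mean reported rate of 39.5% and coverage of 75%. A true 40% gives coverage of 90%.

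**True rates that vary between histologies.** With p ~ Beta(1,3) (mean 25%) and n1 = 3/5/8, the mean reported rate is 70.0/60.0/51.3%, against a mean true rate in opened cohorts of 57.1/50.0/43.8%. The excess is 12.9/10.0/7.5 points, with coverage 80/85/87%. With p ~ Beta(2,6) (also mean 25%) the excess is 16.4/12.9/9.6 points, with coverage 73/80/85%. Unselected coverage is 91%.

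**How the trigger is read.** These are illustrations at a true 25%, n1 = 3/5/8. If 20% of final responses arrive after the six-cycle window, the mean is 47.5/44.9/41.3%. If 20% of triggering responses are not confirmed centrally, it is 41.5/38.2/34.0%. The bias is upward in both.

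**A bound that needs no value of n1.** If the triggering responses stand, T is at least 3. The rate cannot then fall below 30%, nor the lower limit below 12.7%, so the interval can never contain a true rate under 12.7%.

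**The case against.** The strongest reply is that the plan is open about the selection. It states the trigger, the pooling and the minimum of 3 responses, it promises precision rather than freedom from bias, and it attaches no decision to the 10-patient interval. Most of that is right. But 11.3 mentions the 3 responses to justify calling the cohort worthy of further study, not to warn that the rate and interval are affected, and a published 10-patient rate would not carry the caveat with it.

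A second reply is that a true 25% shows coverage at its worst. The lower limit for 5/10 sits just above 25%, so every result from 5/10 upward misses. At 30%, coverage with n1 = 5 or 8 is 77% or 89%. This stands for coverage but not for the rate, which is still 17 or 12 points too high there.

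Third, the worst figures belong to cohorts that rarely open: at a true 25% and n1 = 3 the chance is 1.6%. This also stands, and the opening-weighted figures are the better summary of that case.

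Fourth, the new-patient estimate is thinnest where opening is likeliest: 2 patients at n1 = 8, none at n1 = 10. That is true and limits what the separate rate can add. It does not weaken the case for labelling the pooled one.

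**Conclusion.** The concern holds. Whenever a cohort opens with the triggering patients counted in it, the pooled rate overstates activity on average. The direction was the same in every scenario examined; the size rests on assumed values of n1 and the true rate. At a true 25% the excess runs from 22.5 points (n1 = 3) to 11.9 points (n1 = 10). At a true 40% it runs from 18 points (n1 = 3) to about 5 (n1 = 10), with 9 at n1 = 7. Undercoverage is serious only when the true rate is low or n1 is small, and is gone at a true 40% with n1 of 7 or more.

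The error rates of the primary rule are not touched, and an opened cohort does satisfy the 3-of-20 criterion. This is a reporting weakness in the expansion estimate, worth considering rather than essential.

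**What to change.** Add to 11.3.2 and 11.4:

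1. Report responders by phase: primary-cohort patients of the histology, and patients enrolled after opening.
2. Give the response rate and Wilson 90% interval separately for patients enrolled after opening, whom the trigger does not select.
3. Keep the pooled 10-patient rate and Wilson interval, labelled as selected on at least 3 primary-cohort responders.

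A conditional exact interval for the pooled 10 could be added as a sensitivity analysis, but need not replace anything.

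The cost is a few lines of text and data already collected, with no change to sample size, trigger or decision rule. The drawback is an imprecise extra estimate that will probably look less favourable. It rests on 7, 5 or 2 patients for n1 = 3, 5 or 8; for example, 2/7 gives 10–59%, 1/5 gives 5–57% and 1/2 gives 12–88%. With n1 = 9 it rests on one patient, and with n1 = 10 it does not exist. For n1 of 8 or more, the label in item 3 does most of the work.

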#### 11.4 **Methods of Analysis**

Response criteria are described in [Section 12](#). A responder is defined as a patient who achieves a best response of PR or CR on the study. Response rates will be calculated as the percent of evaluable patients who are responders, and confidence intervals will be constructed using the Wilson score interval method. Decision making for A'Hern design cohorts will follow rules described above.

Toxicity tables will be constructed to summarize the observed incidence by type of toxicity and grade. A patient will be counted only once for a given toxicity for the worst grade of that toxicity reported for that patient. Toxicity information recorded will include the type, severity, time of onset, time of resolution, and the probable association with the study regimen.

#### 11.5 **Evaluability for Response**

Any eligible patient who is enrolled and receives at least one dose of protocol therapy will be considered evaluable for response. Any patient who receives non-protocol anti-cancer therapy during the response evaluation period will be considered a non-responder for the purposes of the statistical rule, unless they show an objective response prior to receiving the non-protocol anti-cancer therapy (in which case they will be considered a responder). Patients who demonstrate a complete or partial response confirmed by central review will be considered to have experienced a response. When opening expansion cohorts, the evaluation period for determination of best response will be the first 6 treatment cycles. All other patients will be considered non-responders. Patients who are not evaluable for response evaluation may be replaced for the purposes of the statistical rule. All patients considered to have a response (CR or PR) must have imaging studies reviewed centrally at the COG. Centers will be notified by the COG about requests for scans of patients with stable disease. Preliminary assessment of activity using institutionally provided tumor measurements will be entered into CDUS quarterly. The central review by COG will be provided as the final reviewed assessment of response when such becomes available.

